4 STUDY SUBJECTS AND ANALYSIS POPULA-TIONS

4.1 Eligibility

This study is among children on ECMO. The exact eligibility criteria are specified in the study protocol.

4.2 Populations for Analyses

4.2.1 Screening Population

The SCREENING population is all patients on ECMO under age 18.

4.2.2 Inclusion Population

The INCLUSION population is all patients who meet all study inclusion criteria and were entered into the study database.

4.2.3 Eligible Population

The ELIGIBLE population is the subset of the INCLUSION population who were determined to meet all eligibility criteria. Note that this will include participants who provided consent but were later found to be ineligible. For the purposes of evaluating the exclusion criterion "on ECMO for > 24 hours at time of enrollment," an unconsented patient who otherwise satisifies all eligibility criteria will be considered eligible if the person would have been eligible to be randomized within 24 hours of cannulation, had the patient been consented. Furthermore, the exclusion criterion "decision to withdraw or withhold some critical care or interventions" will be assumed to not apply unless such a decision was known to be in place (e.g., a participant cannot withdraw if the participant was never consented, but for purposes of determining missed eligibles the person would be counted as eligibile if all other criteria would indicate eligibility).

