The adjudication committee will evaluate patients who are deemed by site investigators to meet this endpoint (severe bleeding or clotting) in batches of 5 patients. The adjudicators will rotate, which will help prevent bias and ensure that all adjudicators have an equal opportunity to contribute to the study. We will report the inter-rater reliability (Kappa) at the end of the study. The committee will make determinations for whether bleeding was the primary cause of the worsening clinical outcome or if clotting was severe. Specifically, the sites will complete the severe bleeding/clotting daily worksheet (see Appendix E) on a daily basis. If a severe bleeding event, or clotting event, the event will be recorded in the database (and the intervention will stop for that participant since this safety outcome has been reached). Once five new patients have any of these events reported, the adjudication committee will review the events and report if they agree with the determination of the outcome within 72 hours of their review or if they need additional information from the site PI. Patient enrollment will continue during their reviews.

B. Secondary Outcomes

Our second objective is to demonstrate the ability for observed endpoints to satisfy various prespecified feasibility thresholds. The information the pilot trial will provide is both necessary and sufficient for the implementation of the full clinical trial. Based on PALISI and BloodNet's suggestions, we will seek further funding and progress to the full trial if at least 5 of the following 10 criteria are met:

- 1. Estimated separation in mean pre-transfusion platelet count is $> 30 \times 10^9$ cell/L;
- 2. Eligibility rate is > 50% of the predicted eligibility rate of 7.9 patients per site per year;
- Proportion of patients whose parents were approached for consent within 24 hours of cannulation (number of patients approached / number of patients eligible for consent) > 90%;
- Proportion of patients for whom we were able to obtain informed consent (number of patients consented / number of patients approached) > 50%;
- 5. Randomization of consented patients is > 66%;

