4.2.4 Approached Population

The APPROACHED population is the subset of the ELIGIBLE population for whom the parents were approached for consent within 24 hours of cannulation.

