4.2.5 Consented Population

The CONSENTED population is the subset of the ELIGIBLE population for whom informed consent for study participation was provided.

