4.2.6 Intention-to-Treat Population

The Intention-to-Treat (ITT) population is the subset of the CONSENTED population who were randomized to one of the study's two transfusion thresholds. For the ITT population, the treatment arm is the arm to which the participant was assigned, even if this strategy was not adhered to or there was a randomization error because the wrong randomization stratum was used. The ITT population will equivalently be regarded as the ENROLLED population. Note that a participant who consented and was randomized but was later found to be ineligible will still be considered part of the ITT population for analysis and safety assessment purposes. Although we note that the primary analysis of the primary outcome requires being in the ITT population as a necessary condition, not all ITT participants will necessarily contribute to the primary analysis because the primary outcome is a transfusionlevel outcome and as such is not applicable if an ITT participant had no transfusions during the acute follow-up period. (Additionally, note that missing primary outcomes from ITT participantes with transfusions will not be imputed.)

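### SAP 4.2.3 has no common eligibility rule for consenters and refusers: read with SE5's rationale the consent rate (SE4) is biased upward, read with 4.2.2 SE5's 66% bar loses its basis, and the one reading that saves both is not stated.

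*Combined protocol and SAP*

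**What the plan says.** **Protocol 9.B.** Criterion 3 divides patients approached by patients eligible for consent. Criterion 4 is: "Proportion of patients for whom we were able to obtain informed consent (number of patients consented / number of patients approached) > 50" per cent. Criterion 5 asks that more than 66% of consented patients be randomized.

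**SAP 2.2.2.** SE4 is CONSENTED over APPROACHED. SE5 is ITT over CONSENTED, and its 66% bar is explained by earlier data in which about one-third of patients bled within 24 hours of cannulation.

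**SAP 4.2.2 to 4.2.5.** The populations are nested:
- "The INCLUSION population is all patients who meet all study inclusion criteria and were entered into the study database". Protocol 6.D makes no or minimal bleeding within 24 hours of cannulation an inclusion criterion, and admits children whose heavier bleeding settles in that time.
- ELIGIBLE is the part of INCLUSION determined to meet all eligibility criteria. For consenters the SAP adds: "Note that this will include participants who provided consent but were later found to be ineligible".
- For the exclusion of children more than 24 hours on ECMO, an unconsented child who otherwise qualifies "will be considered eligible if the person would have been eligible to be randomized within 24 hours of cannulation, had the patient been consented".
- The exclusion for a decision to withdraw or withhold care "will be assumed to not apply unless such a decision was known to be in place".
- "The APPROACHED population is the subset of the ELIGIBLE population for whom the parents were approached for consent within 24 hours of cannulation".
- "The CONSENTED population is the subset of the ELIGIBLE population for whom informed consent for study participation was provided".

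**SAP 4.2.6.** The similar note for ITT is narrower. It covers "a participant who consented and was randomized but was later found to be ineligible".

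**The concern.** Families may be asked before bleeding status is settled: protocol 7.A plans to seek consent before cannulation where possible, and otherwise within 24 hours of it. A child can therefore look eligible at the approach and then bleed until the window closes. If the family consented, the note in 4.2.3 appears to keep the child in ELIGIBLE and CONSENTED. If the family refused, no such note applies, and a child who never met the bleeding criterion falls outside INCLUSION and so outside APPROACHED. SE4 would then depend partly on who bled and not only on what families answered.

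Consent is one of the ten feasibility criteria. Under protocol 9.E the pilot's experience with standard consent also informs whether the full trial needs an exception from informed consent. That second use needs families' answers undistorted.

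**Working it through.** **1. The plan's own figure.** SE5's bar: 1 - 1/3 = 66.7%, which matches 66%. This holds only if consented children who bleed, and so are not randomized, are counted in CONSENTED. The note in 4.2.3 allows that, since unlike the note in 4.2.6 it does not require randomization.

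**2. Consented bleeders stay in, matching refusers drop out.** Let c be true consent among approached families. Let b be the share of approached children with no randomizable window, assumed equal in consenters and refusers. Then

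SE4 = c / [c + (1-c)(1-b)],

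which equals 50% at c = (1-b)/(2-b). The documents give no value for b, so a range is shown:

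| b (assumed) | True consent at which SE4 reaches 50% | SE4 when c = 45% |
|---|---|---|
| 0 | 50.0% | 45.0% |
| 5% | 48.7% | 46.3% |
| 10% | 47.4% | 47.6% |
| 20% | 44.4% | 50.6% |
| one-third | 40.0% | 55.1% |

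The last row is an outer limit, not an estimate. One-third is the share who bleed; some of them settle within 24 hours, and a refuser who was randomizable at any moment stays in.

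**3. Without assuming b.** With A approached and C consenting, the result moves from fail to pass once more than A - 2C refusers are left out. As a convenient scale take A = 143, just over 90% of 2 x 79 = 158. If C = 70, true consent is 70/143 = 49.0%. A - 2C = 3, so leaving out 4 of the 73 refusers gives 70/139 = 50.4%. If C = 68 (47.6%), A - 2C = 7, and leaving out 8 of 75 gives 68/135 = 50.4%.

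**4. Chance of passing near the bar.** Take C as binomial (143, 0.46) and the refusers kept as binomial (143 - C, 1 - b); SE4 passes if C exceeds the refusers kept. The probability is 17% at b = 0, 25% at b = 5% and 36% at b = 10%. The value 46% was chosen to lie close to the bar; well away from it the rule matters much less.

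**5. Consented bleeders also removed under 4.2.2.** With equal b the factor (1-b) cancels and SE4 = c. SE5's bar then means something else. With one-third of consented children lost to bleeding, it leaves room for 1 - 0.66/(2/3) = 1% loss among the rest. With bleeders outside the denominator it tolerates 1 - 0.66 = 34% loss for reasons the SAP does not mention.

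**6. Eligibility fixed at the screening determination for everyone.** Later bleeding removes neither consenters nor refusers. SE4 = c, and SE5 is expected at 66.7%. Both criteria work as intended.

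**The case against.** The strongest reply is the reading in step 6. SAP 4.2.3 speaks of patients determined to meet the criteria, and SE2 treats eligibility as a status recorded in the database for each screened patient. The note on consenters may then say only that nobody is removed retroactively, with the same true of refusers. This fits the text. A reader might infer that one criterion is flawed however the SAP is read; the documents do not support that. What remains is that 4.2.2 to 4.2.5 give no time point for the determination, and the protection against later removal is written for consenters alone.

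The sentence on unconsented children serves the 24-hour ECMO exclusion and says if, not only if, so it is not itself a bleeding filter. That is correct. The loss of refusers comes from 4.2.2, and only when its bleeding criterion is judged over the whole 24 hours.

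A reader might also infer that the SAP departs from the protocol by nesting APPROACHED in ELIGIBLE. It does not: protocol criterion 3 already places approached patients within those eligible for consent. The departure arises only if refusers are taken out after the approach.

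The size is assumed. The value of b is unknown, and 158 is already a count of eligible patients, so 143 is a scale and not a forecast. The withdraw/withhold rule keeps some unconsented children in and may offset part of the rise, so the net direction is not established. Finally, the screening log and the planned reporting of approach and consent would allow a recalculation. That softens the consequence but does not settle which figure decides the criterion.

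**Conclusion.** The point holds as an unequal and undated eligibility rule. Read with SE5's rationale, the mechanism raises SE4 for any b above zero and lowers the effective bar on true consent to 48.7% at b = 5% or 47.4% at b = 10%. This assumes that bleeding without a randomizable window is as common in consenters as in refusers. Read with 4.2.2 applied to both groups, SE4 is symmetric and SE5's 66% has no stated basis. Only a determination fixed at screening for everyone leaves both sound, and the SAP would have to say so.

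It would be too strong to infer that the consent rate will be overstated by 10 points (50% reported as 60%). That takes b = one-third, which the documents do not support. Nor does the point overturn the go decision: one of ten criteria is affected and five suffice. The remaining stake is the consent evidence for the decision on exception from informed consent. The point is worth correcting, with medium confidence in its practical effect.

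**What to change.** In SAP 4.2.3 to 4.2.5, fix eligibility for SE3, SE4 and SE5 at one time point for consenters and refusers alike: eligible for consent when the family is approached, in line with protocol 9.B criteria 3 and 4. State that neither group is removed for bleeding found later, and how this fits with 4.2.2. SE4 is then consented over approached, approached has one meaning in SE3 and SE4, and SE5's 66% keeps its one-third basis. The eligible count for SE2 can stay separate and unchanged.

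The cost is SAP wording. The screening log in protocol 7.A already records patients eligible for consent but not randomized, bleeding between cannulation and enrollment, and reasons for exclusion. The drawback is that the reported consent rate may be slightly less favourable.

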4.2.4 Approached Population

The APPROACHED population is the subset of the ELIGIBLE population for whom the parents were approached for consent within 24 hours of cannulation.

4.2.5 Consented Population

The CONSENTED population is the subset of the ELIGIBLE population for whom informed consent for study participation was provided.

4.2.6 Intention-to-Treat Population

The Intention-to-Treat (ITT) population is the subset of the CONSENTED population who were randomized to one of the study's two transfusion thresholds. For the ITT population, the treatment arm is the arm to which the participant was assigned, even if this strategy was not adhered to or there was a randomization error because the wrong randomization stratum was used. The ITT population will equivalently be regarded as the ENROLLED population. Note that a participant who consented and was randomized but was later found to be ineligible will still be considered part of the ITT population for analysis and safety assessment purposes. Although we note that the primary analysis of the primary outcome requires being in the ITT population as a necessary condition, not all ITT participants will necessarily contribute to the primary analysis because the primary outcome is a transfusionlevel outcome and as such is not applicable if an ITT participant had no transfusions during the acute follow-up period. (Additionally, note that missing primary outcomes from ITT participantes with transfusions will not be imputed.)

4.2.7 Safety Population

The SAFETY population is comprised of all patients in the ITT population. In the unlikely event that a participant is randomized but did not have informed consent provided, this person will be added to the SAFETY population. All individuals in the SAFETY population will be analyzed according to the assigned treatment arm. This population will be used for adverse event summaries and for the primary safety outcome's interim and end-of-study analyses.

5 GENERAL ISSUES FOR STATISTICAL ANALY-SES

5.1 Analysis Software

Analysis will be performed using SAS® Software version 9.4 or later when feasible. Other software packages, including R and StatXact®, may be used for particular specialized procedures.

5.2 Methods for Withdrawals, Missing Data, and Outliers

Participants who withdraw from the study intervention should continue to be followed for assessment of safety outcomes, if allowed. However, outcomes such as the primary outcome of pre-transfusion platelet counts and adherence to study intervention will be ignored from analyses beginning at the time of the withdrawal.

Because the outcomes generally relate to adherence or outcomes that should have no missingness (e.g., whether or not a patient consented), it is not expected that missing data will be problematic for the main analyses. There is naturally some protection against detrimental effects due to missing data for model-based analyses that incorporate random effects or other forms of within-subject correlation, such as for the primary outcome.

Outliers may affect the primary analysis because the primary analysis of Aim 1 is meanbased. Pre-transfusion platelet counts that appear to be outliers may be queried to ascertain if the values were correctly recorded. If it is determined that the values were not correctly recorded, they will be corrected if the correct values are available. If it is determined the values were not correctly recorded but the correct values are unavailable, the platelet counts will be regarded as missing for the primary Aim 1 analysis of separation in mean platelet counts.

5.3 Multiple Comparisons and Multiplicity

The first objective has one primary analysis: separation in the average pre-transfusion platelet counts between treatment strategies. There is an associated one-sided test to be conducted at $\alpha = 0.025$. This test provides the key p-value for purposes of the Aim 1 feasibility assessment.

Other tests of the feasibility, including the one-sided test for separation in the average total volumes of transfusions, are considered supplementary or exploratory and as such will not

be adjusted for multiple comparisons.

The early stopping rule for safety allows multiple tests and as such will account for multiplicity as described in Section 6.

5.4 Planned Subgroups, Interactions, and Covariates

Subgroups defined by the randomization strata (≤ 28 days vs > 28 days) will be considered. The intended sample size does not facilitate precise subgroup inference, so subgroup analyses will be considered as supplementary and interpreted carefully. We do not plan to allow for interactions in exploratory models given there is limited information for estimation of even main effects. ECMO type (Veno-Venous [V-V] vs Veno-Arterial [V-A]) may be used as a covariate in some exploratory analyses, and site may be included as a random effect in some exploratory analyses.

5.5 Derived and Computed Variables

Derived variables needed for analysis will be defined in a corresponding data dictionary. Most variables of particular importance were already defined. Select variables of particular importance are defined in the remainder of this subsection.

Additional outcomes: transfusion volumes in mL/kg/run and mL/kg/day. These are the total platelet transfusion doses while on ECMO in mL/kg/run, and the transfusion dose in mL/kg/hr (or its redundant value, in mL/kg/day, obtained by multiplying the dose in mL/kg/hr by 24). When determining the total mL/kg of the platelet transfusions, all doses given from randomization until the permanent discontinuation of the transfusion strategy will be counted, whether or not the dose was transfused during a temporary suspension of the assigned strategy. The total transfusion dose measured in mL/kg/run is simply the mL/kg during this acute follow-up phase, whereas the dose in mL/kg/day is the total dose in mL/kg divided by the number of hours from randomization until permanent strategy discontinuation.

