 It will be possible to consider the pilot ECSTATIC trial as a vanguard phase of the full RCT and to merge their data to the data of the patients enrolled in the full trial if no significant changes are made to the design of the full RCT. On the other hand, merging patients of the pilot and the full trials would be inappropriate if significant changes are made (e.g., the threshold platelet count is changed). In that case, we will combine the data of the pilot and of the full RCT by performing a meta-analysis.

11. Study Monitoring and Study Organization

Approval for use of this protocol by the Human Studies Committee (HSC) must be obtained in accordance with the institutional assurance policies of the U.S. Department of Health and Human Services. Institutional Review Board (IRB) approval of the ECSTATIC protocol and consent forms will be required prior to patient participation on the trial. The single IRB at BRANY will coordinate IRB approvals at each site within the United States. All reasonable measures will be taken to protect the confidentiality and identity of the patient and patient's records according to State and Federal laws. Patient identity will not be revealed in any publication.

A. Study Monitoring

Data will be collected at PICU entry (e.g., PRISM and PELOD-2 scores, co-morbidity, coagulation evaluation, etc.), at ECMO cannulation, at randomization, daily while patient is on ECMO, at ECMO end, and at PICU discharge. Data will be collected at least on a daily basis from ECMO initiation to ECMO end. Mortality (28-day and 90-day) is the only data that would be collected after PICU discharge. The application of the RCT protocol (lower or higher platelet threshold strategy) will end at the earliest of any of the following five events: (1) progression to severe bleeding, according to the BASIC definition, and/or severe clotting, and/or death; (2) decannulation from ECMO; (3) Twenty-one days post-randomization (as the progression to new bleeding and new thrombosis has plateaued by day 21 and 95% of the patients will be off ECMO by then); 4) temporary suspension lasting more than 24 hours; or 5) study withdrawal.

Data management will include an audit trail, a security system, query functionality and quality control done according to US CFRs. Data management will be performed at the Trial Innovation Network at the University of Utah under the supervision of the study statistician.

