Preliminary data from the BATE study suggests about 65% of the non-bleeding patients will experience severe bleeding, severe clotting, and/or death (6). Each ml/kg of platelet transfusion was independently associated with 1% increased odds of bleeding and 5% increased odds of mortality. Considering the median dose is 92 ml/kg per ECMO run and a low platelet threshold transfusion strategy is expected to decrease blood exposure by at least 20%, the effect of the low platelet threshold strategy may be a 17% relative decrease in the odds of bleeding [(1/1.01) odds ratio for each 1 ml/kg reduction and median reduction of 20% x 92 ml/kg), i.e., an absolute risk reduction in percentages from 65% to approximately 60.7%. These results, which are extrapolated from observational data where no transfusion strategies were enforced, **need to be confirmed in the pilot trial**.

Non-inferiority margins of safety of 5% and 10% (33) have previously been used in transfusion medicine. With a margin of 5% and based on these very uncertain data, if there is a true relative difference in favor of the low platelet threshold strategy of 6.6% (i.e., 65% vs 60.7% progression to severe bleeding and/or severe clotting), and we anticipate a 5% drop-out rate (similar to what was observed in previous studies), using an alpha of 0.025 and a 90% power, **the sample size to enroll for the test of non-inferiority would be 1238 patients (619 per arm)**, The primary outcome would be ascertained for an expected 588 per arm. We will calculate the 95% confidence intervals (95% CI) around the absolute risk reduction in the proportion of patients progressing to severe bleeding and conclude non-inferiority if the upper limit of the 95% CI is lower than 5%. For example, if the proportion of patients who progress to the primary outcome is 376/588 (64%) in the higher platelet threshold group and 359/588 (61%) in the lower platelet threshold group, the absolute risk reduction would be 3%, but the 95% CI would be -9% to 3%. In this example, although superiority would not have been demonstrated (p=0.34), we could conclude to a non-

inferiority as the upper limit of the absolute risk reductions (+3%) is below the +5% pre-defined limit of the margin of safety.

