2.2 Study Outcomes

2.2.1 Primary Outcome(s)

The **primary outcome for Aim 1**, hereafter *primary outcome*, is the platelet count immediately (or as recently as available) before a transfusion. Note that this outcome is defined for each transfusion, and as such, participants may contribute multiple values.

Though not considered primary outcomes, there are two outcomes that are especially related to the primary outcome which are of additional interest: the total platelet transfusion dose while on ECMO in mL/kg/run, and the transfusion dose in mL/kg/hr (or its redundant value, in mL/kg/day, obtained by multiplying the dose in mL/kg/hr by 24). Refer to Section 5.5 for details of the mL/kg/run and mL/kg/hr calculations.

For safety monitoring, there is a **primary safety outcome**, (occurrence of progression to severe bleeding, severe thrombosis, or death, in the acute follow-up period more precisely defined in Section 2.2.5). To avoid confusion, any reference to the primary safety outcome contains the qualifier "safety."

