2.2.5 Safety Outcome(s)

Many safety outcomes are obtained during the *acute follow-up period*, defined as the period beginning with randomization and ending 24 hours after the permanent discontinuation of the transfusion strategy. The transfusion strategy for a randomized patient is permanently discontinued at the earliest of any of the following five events: (1) per site report, progression to severe bleeding, according to the BASIC definition, and/or severe clotting, and/or death; (2) decannulation from ECMO; (3) twenty-one days post-randomization (as the progression to new bleeding and new thrombosis has plateaued by day 21 and $\approx 95\%$ of the patients will be off ECMO by then); 4) temporary suspension lasting more than 24 hours; or 5) study withdrawal.

The primary safety outcome is defined at the patient level for all patients in the ITT population. It is defined as the occurrence of any of the following during the acute follow-up period: progression to severe bleeding (defined below); progression to severe thrombosis (defined below); death. The outcome is initially site-reported but then is to be adjudicated by the adjudication panel. If the panel determines the outcome criteria were not met, the outcome will be considered not to have occurred. Otherwise, if the panel confirms the criteria were met, or if the panel is unable to reach a determination, the primary safety outcome will be considered to have occurred.

Using the BASIC definition [2], severe bleeding will be defined as:

- 1. Bleeding that leads to at least one organ dysfunction, using PELOD-2 score criteria of organ dysfunction
- 2. Bleeding that leads to hemodynamic instability, defined as an increase in heart rate (HR) by > 20% from baseline or a decrease in blood pressure (BP) by > 20% from baseline (i.e., prior to the bleeding event)
- 3. Bleeding leading to a drop in hemoglobin >20% within 24hr
- 4. Quantifiable bleeding $\geq 5 \text{ mL/kg/hr}$ for $\geq 1 \text{hr}$ (e.g., chest tube)
- 5. Intracranial hemorrhage on computerized tomography (CT) scan or head ultrasound
- 6. Intraspinal bleeding leading to loss of neurologic function below the lesion, nontraumatic intra-articular bleeding leading to decreased range of movement, or intraocular bleeding leading to impaired vision.

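### The per-run platelet dose (mL/kg/run) is really an on-strategy total: severe bleeding or clotting can cut it off before ECMO ends, and SAP 5.5 gives its window two different ends

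*Combined protocol and SAP*

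**What the plan says.** SAP 2.2.1 lists, as an outcome related to the primary one, "the total platelet transfusion dose while on ECMO in mL/kg/run". Protocol 9.A likewise describes platelet dose collected while the patient is on ECMO, with days on ECMO as the divisor for the daily figure.

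SAP 5.5 sets the counting rule: "all doses given from randomization until the permanent discontinuation of the transfusion strategy will be counted". It continues: "The total transfusion dose measured in mL/kg/run is simply the mL/kg during this acute follow-up phase". SAP 2.2.5 gives that phase a different end, since it is "defined as the period beginning with randomization and ending 24 hours after the permanent discontinuation of the transfusion strategy".

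The first of the five events that discontinue the strategy in SAP 2.2.5 is "per site report, progression to severe bleeding, according to the BASIC definition, and/or severe clotting, and/or death". Protocol 8.H makes one exception, for a severe event that arises in a temporary suspension and resolves within 24 hours.

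SAP 7.2.2 compares arms by the difference in median mL/kg/run with a bootstrap 95% interval. It adds mL/kg/day to allow for different times on strategy. No whole-run volume is specified. Blood product exposure (protocol 9.D, SAP 2.2.4) counts transfusions, not mL/kg.

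Appendix A (Sample Size) builds the full-trial effect on an expected 20% cut in exposure, where "the median dose is 92 ml/kg per ECMO run", and says its extrapolated results need confirmation in the pilot.

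**The concern.** A child with non-fatal severe bleeding or clotting leaves the strategy but can stay on ECMO and keep receiving platelets. Those platelets drop out of a variable labelled per run. The cut-off is not neutral, because severe bleeding and clotting are outcomes that the threshold may change. The two arms may therefore be truncated at different times for reasons related to treatment. Other things equal, the arm with more or earlier severe events shows the smaller total, which could be read as a platelet saving.

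Two further problems follow. A strategy-truncated total is not the per-run exposure that Appendix A uses. And with two window ends in adjacent sentences, the two statisticians who program the results under SAP 5.6 could both follow the text and obtain different totals.

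**Working it through.** **1. The plan's own figures.** Appendix A: 0.20 × 92 = 18.4 mL/kg; odds ratio (1/1.01)^18.4 = 0.833; odds 0.65/0.35 = 1.857; 1.857 × 0.833 = 1.546; risk 1.546/2.546 = 0.607. The stated fall from 65% to 60.7% reproduces. The power of about 81% (SAP 8) also reproduces: a difference of 30, SD 40 and 30 effective observations per arm give 82.8% by the normal approximation and 81.5% by the noncentral t. That figure concerns platelet counts and is untouched here. The documents give no expected value or power for mL/kg/run.

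**2. Time on strategy.** Assume a constant hazard λ of leaving ECMO, equal in the two arms, and a constant hazard h of a severe event that ends the strategy. Then P = h/(h + λ), and mean time on strategy = 1/(h + λ) = (1 − P)/λ. The median scales by the same factor. A full run averages 1/λ.

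**3. Apparent per-run contrast.** Suppose the lower-threshold arm truly has a 20% lower daily dose. Treat Appendix A's rates as non-fatal events.
- Higher arm 65%, lower arm 60.7%: 0.8 × 0.393/0.35 = 0.90, about 10% lower.
- Rates swapped: 0.8 × 0.35/0.393 = 0.71, about 29% lower.

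With the 21-day cap and mean runs of 5, 8 and 12 days, the factor 0.35/0.393 = 0.89 becomes 0.891, 0.891 and 0.895.

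**4. Simulated medians.** 400,000 children per arm; exponential runs with 95% off ECMO by day 21; the same daily dose in both arms, 18.9 mL/kg/day, chosen so that the whole-run median is 92 mL/kg.

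| Severe events, arm 1 v arm 2 | On-strategy median (mL/kg) | Apparent difference |
|---|---|---|
| 60.7% v 65% | 36.0 v 32.3 | −10% |
| 45% v 55% | 50.5 v 41.3 | −18% |
| 40% v 60% | 55.0 v 36.8 | −33% |

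Whole-run medians stay at about 92 in every row, and mL/kg/day is 18.9 v 18.9. The last two rows use assumed rates.

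**5. Deaths.** The 65% includes death, and death on ECMO ends the run as well as the strategy, so it truncates nothing. Removing an assumed 10 points per arm gives 0.8 × 0.493/0.45 = 0.88 (12% lower). Removing 20 gives 0.8 × 0.593/0.55 = 0.86 (14% lower). Swapped, the results are 27% and 26% lower. The distortion shrinks but keeps its direction.

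**6. The two window ends.** At the assumed 18.9 mL/kg/day, a child who remains on ECMO gains 18.9 mL/kg if the extra 24 hours are counted. The on-strategy medians in the first row are 32 to 36 mL/kg.

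**7. The whole-run total.** Assume equal daily use in both arms after the event. With 60.7% events in the lower arm, the fraction of ECMO time on strategy is 0.393, so the ratio is 0.393 × 0.8 + 0.607 = 0.92, about 8% lower. With 65% it is 0.35 × 0.8 + 0.65 = 0.93, about 7% lower.

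**The case against.** The strongest reply is that separation while the strategy applies is what a pilot should measure. Aim 1 anticipates a 20% difference in average daily dose over exactly that window, and mL/kg/day already allows for its length. This stands: the daily dose shows no spurious difference in step 4. It does not repair the label or the conflicting window, and it says nothing about platelets given after discontinuation.

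Nor is the whole-run total a cleaner replacement. In step 7 it shrinks a true 20% reduction to about 8%, no closer to the truth than the 10% in step 3. It also includes therapeutic platelets given after a severe bleed. If daily use doubled after the event, whole-run medians at 40% v 60% events would be about 105 v 122, against on-strategy medians of 55 v 37, so the order reverses. The two totals answer different questions. This stands, and it is why both are needed.

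Third, precision is poor. The historical interquartile range of 42 to 239 mL/kg (protocol 5.B) implies a log-SD of about ln(239/42)/1.349 = 1.29 if lognormal. With 25 per arm, the 95% interval for a ratio of medians then runs from roughly 0.41 to 2.45, against which an 11% shift is small. That limits what the pilot can show but does not settle what is being estimated.

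Finally, the Appendix A comparison is loose. The 92 mL/kg is described once as over ECMO support (protocol 5.A) and once as over the admission (5.B). A total starting at randomization also omits doses given earlier on ECMO.

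**Conclusion.** The SAP labels as a whole-run dose what its counting rule makes an on-strategy dose, and it states two ends for the window. Time on strategy depends on a safety outcome, so the arm difference in mL/kg/run mixes platelet use with event timing. In the illustration, a true 20% daily reduction appears as about 10% or 29% lower. This rests on constant hazards, equal run lengths in the arms, and composite rates taken as non-fatal, which is an upper bound.

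A reader might infer that the arm with more severe events must look platelet-sparing. The documents do not support that: in the 40% v 60% example, about 1.5 times the daily use before the event in the higher-event arm would cancel the effect, and some events during suspensions do not end the strategy. A reader might also infer that the pilot's main conclusion is at risk. It is not. SAP 2.2.1 says that the dose outcomes are not primary, SAP 5.3 treats the volume comparison as supplementary, and none of the ten feasibility criteria uses it. The primary outcome and its power are unaffected.

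**What to change.** In SAP 5.5:

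- Name the existing total on-strategy dose (mL/kg) and state one end point for its window.
- Derive mL/kg/run as the total from randomization to the end of the ECMO run (decannulation or death on ECMO). Report both totals by arm with the bootstrap interval already planned.
- Report time on strategy and reason for discontinuation by arm, and read the on-strategy total alongside mL/kg/day.
- Confirm that platelet volumes are captured to the end of ECMO. Protocol 11.A says "Data will be collected at least on a daily basis from ECMO initiation to ECMO end", but the abstract describes daily follow-up only to 24 hours past the strategy's expiry.

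The same edit should reconcile protocol 9.A, which ignores transfusions during temporary suspensions for the dose outcomes, with SAP 5.5, which counts them.

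The cost is SAP wording and one derived variable, provided the volumes are captured. The downside is that the whole-run total includes unrestricted and therapeutic transfusions after discontinuation, which dilutes the strategy contrast. It should complement the on-strategy comparison and not replace it.
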